## **Safety Analysis**

Safety will be assessed by descriptive statistics of AEs and laboratory tests. The incidence of reported AEs and the values of laboratory tests from all subjects will be presented with and without regard to causality based on the Investigator's judgment.

Adverse events will be coded according to MedDRA and presented in tables by system organ class, MedDRA preferred term and study group. Adverse events will be summarized by treatment group to provide visual comparison among the treatment groups with respect to incidence of adverse events (the number of subjects reporting at least one episode of a specific adverse event), incidence of adverse events by severity within body system, incidence of adverse events by attribution within body system, and incidence of adverse events causing withdrawal and incidence of serious adverse events. Regarding severity and attribution summaries, the most extreme outcome (highest severity and closest to study drug related) will be used for those subjects who experience the same adverse event on more than one occasion.

Written narratives will be provided for all serious, unexpected or other significant adverse events that are judged to be of special interest because of their clinical importance.

Chi-square test or Fisher's Exact test (as appropriate) will be applied for testing the statistical significance of the difference in percent of subjects reporting adverse events between the study groups.

Paired T-Test or Signed Rank test (as appropriate) will be applied for testing the statistical significance of the changes from baseline in laboratory results within each study group.

ANOVA model will be applied for testing the statistical significance of the difference in the changes in laboratory results between the study groups. Dunnett's method will be used for comparing each of the active groups to the Placebo group. Adverse Events

All tests will be two-tailed, and a p value of  $\leq 5\%$  will be considered statistically significant.

The data will be analyzed using the SAS ® version 9.1 (SAS Institute, Cary North Carolina).

The measurement of serum bovine and anti-LPS antibody levels at baseline, Day 7, and Day 28-30 of dosing with test colostrum/placebo, and the fold increases over baseline will be assessed. Typically, an antigenic response is defined as 4-fold above baseline. A specialist laboratory can utilize commercially available ELISAs to measure for the presence of serum anti-bovine and anti-LPS IgGs, such as the bovine IgG ELISA kit from Genway (no reactivity with IgG from mouse, human, rat and rabbit) and human LPS ELISA kit from Cusabio, respectively. Samples drawn at baseline, Day 7, and Day 28-30 will then be analyzed, all together, at the end of the study.

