**STATISTICAL ANALYSIS:**

This study is designed to evaluate dose response and appropriateness of endpoints for further work. All measured variables and derived parameters will be listed individually and, if appropriate, tabulated by descriptive statistics. For descriptive statistics, summary tables will be provided giving sample size, absolute and relative frequency by study group and sample size, arithmetic mean, standard deviation, coefficient of variation (if appropriate), median,

minimum and maximum, percentiles, p-values, and 95% CI (Confidence Interval) by study group for means of continuous variables.

**Chi-square test or Fisher's Exact test** (as appropriate) will be applied for testing the statistical significance of the difference in percent of subjects reporting adverse events between the study groups.

**Paired T-Test or Signed Rank test** (as appropriate) will be applied for testing the statistical significance of the changes from baseline in laboratory results within each study group.

**ANOVA model** will be applied for testing the statistical significance of the difference in the changes in laboratory results between the study groups.

**ANOVA model** will be applied for testing the statistical significance of the difference in immunological markers and the secondary endpoint parameters between the study groups.

**Dunnett's method** will be used for comparing each of the active groups to the Placebo group. Changes in immunological markers and efficacy parameters may be assessed across each individual subject.

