**FOLLOW-UP AND POST-STUDY SAFETY TEST PARAMETERS**

**SERUM BIOCHEMISTRY**

Total Protein

Albumin

Total bilirubin

ALT

AST

Alkaline Phosphatase

Glucose

Sodium

Potassium

Calcium

Phosphate

BUN

Creatinine

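### The within-arm significance tests of laboratory change say nothing about Imm 124-E and can mislead; drug statements should rest on a baseline-adjusted comparison of each dose with placebo

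*Combined protocol and SAP*

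**What the plan says.** The Safety Analysis section plans three things for laboratory values.

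- **Within each arm:** "Paired T-Test or Signed Rank test (as appropriate) will be applied for testing the statistical significance of the changes from baseline in laboratory results". The tests are run arm by arm. The Synopsis, under Statistical Analysis, repeats this: the same tests "will be applied for testing the statistical significance of the changes from baseline in laboratory results within each study group".
- **Between arms:** "ANOVA model will be applied for testing the statistical significance of the difference in the changes in laboratory results between the study groups".
- **Each dose against placebo:** "Dunnett's method will be used for comparing each of the active groups to the Placebo group".

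On the level, "All tests will be two-tailed, and a p value of" 5% or less "will be considered statistically significant". The sentence covers all tests and does not exempt the within-arm ones. The section opens by calling the safety assessment descriptive, yet it then specifies these tests.

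Baseline adjustment appears elsewhere. The paragraph on anticipated outcomes, under Data Safety Monitoring Board, says end-of-study means of continuous variables will be analysed by ANCOVA adjusting for baseline. The laboratory ANOVA in Safety Analysis and in the Synopsis is on changes, with no baseline covariate stated.

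**The concern.** A paired test within an arm asks whether patients changed. It does not ask whether the drug changed them. Several features of the design can move laboratory values in all three arms:

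- All arms receive prednisolone or prednisone, nutrition support and alcohol-cessation advice.
- Table 2 schedules the routine laboratory panels at screening (Day -7 to 0) and not at Day 0. If screening is the baseline, change before the first dose counts as change.
- Patients who meet the Lille failure criteria at Day 7 are removed, and the score uses Day 7 bilirubin. If their later values are not collected, bilirubin after Day 7 is selected toward improvement in every arm.

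Three arm-wise p-values printed side by side invite the reading that significance on active but not on placebo is a drug effect. The plan does not warn against this. Its own Introduction also moves from an uncontrolled Day 0 to Day 30 comparison in NASH to a conclusion that the product acts on the immune system. Change in laboratory parameters is a listed secondary endpoint, so both a false signal and false reassurance would matter.

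**Working it through.** **The plan's own figure.** The plan gives no calculation for laboratory safety. Its only sample-size calculation is Table 4, for endotoxin. The normal approximation n = 2(z₁₋α/₂ + z_power)²(SD/difference)² gives 4, 20, 8 and 25 per arm for the four scenarios, against 5, 20, 7 and 26 in the table. Only the chosen arm size, 22, is used below.

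**Inputs.**
- n = 22 in each of three arms (Determination of Sample Size).
- Two-sided 5% tests (Safety Analysis).
- A common mean shift d, in SDs of the change, equal in all three arms, so there is no drug effect. The documents give no value for d; the range 0 to 1.0 is assumed.

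**Formulas.** Let p be the power of the paired t-test at n = 22 for shift d (noncentral t).
- A given active arm significant, placebo not: p(1 − p).
- At least one of the two active arms significant, placebo not: (1 − p)[1 − (1 − p)²].

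For d = 0.4, p = 0.433. The first is 0.433 × 0.567 = 0.245; the second is 0.567 × (1 − 0.567²) = 0.385.

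**Results per parameter and visit.**

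| d (SD) | p | given active arm only | at least one active, not placebo |
|---|---|---|---|
| 0 | 0.050 | 4.8% | 9.3% |
| 0.2 | 0.146 | 12.5% | 23.1% |
| 0.3 | 0.269 | 19.7% | 34.0% |
| 0.4 | 0.433 | 24.5% | 38.5% |
| 0.5 | 0.609 | 23.8% | 33.1% |
| 0.6 | 0.765 | 18.0% | 22.2% |
| 0.8 | 0.947 | 5.0% | 5.3% |
| 1.0 | 0.994 | 0.6% | 0.6% |

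The last column peaks at 38.5%, near d = 0.4. Beyond that it falls, because all arms become significant together. Simulation of 100,000 trials per d, for d from 0.2 to 1.0, agreed with both columns to within 0.3 percentage points.

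**Fewer patients.** The plan gives no dropout rate. With 15 per arm (assumed), the last column is 38.4% at d = 0.5 and 17.3% at d = 0.8.

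**The planned between-arm test.** On the same simulated data, Dunnett's test (pooled variance, 63 df, critical value 2.26) declared at least one dose different from placebo in 4.9-5.1% of trials at every d from 0.2 to 1.0.

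**False reassurance.** At n = 22 a true within-arm change of 0.4 SD is missed with probability 1 − 0.433 = 0.567.

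**Number of tests.** The follow-up list has 13 biochemistry and 9 hematology parameters. If each were tested at Days 7, 30, 90 and 180, there would be 22 × 4 × 3 = 264 within-arm tests. With no change at all, 264 × 0.05 = 13.2 would be significant. Those would be false findings of change from baseline, not of a drug effect, and the documents do not say that every parameter is tested at every visit.

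**The case against.** The strongest reply is that the right comparison is already planned. The sentence after the within-arm tests specifies a between-arm ANOVA, Dunnett's method follows, and ANCOVA is named elsewhere. The Synopsis also promises 95% CIs by group for means of continuous variables. No section says arm-wise p-values will be compared or used to infer a drug effect, and no sample size, stopping rule or primary analysis depends on them; the primary endpoint analysis under Subject Disposition concerns adverse events. All of this stands, and it limits the point to redundant and potentially misleading p-values.

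A reader might also infer that patients enter at a severity peak, so that values must fall back. The documents do not support this. Entry is at MELD 20 to 28, up to 7 days of earlier steroid treatment is allowed, and the notes to Table 1 say bilirubin may still rise. The argument needs only a common shift, in either direction.

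Nor does it follow that the misleading pattern will be frequent whatever happens. A strong common response makes it rare.

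The reply does not show any use for the within-arm p-values. The plan calls them significant at 5%, does not label them descriptive, and already holds the comparison that answers the question about the drug.

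**Conclusion.** The point holds in a limited form. The within-arm tests are an addition to a valid between-arm analysis, not the plan's only laboratory analysis, and the documents do not show an intention to read them as drug effects. They still carry no information about Imm 124-E. With no drug effect and 22 per arm, they give the active-but-not-placebo pattern in about 22-39% of parameter-visits at common shifts of 0.2-0.6 SD. The figure is about 9% at no shift and about 5% or less at 0.8 SD or more. The planned Dunnett comparison gives about 5%. These figures assume an equal shift and equal variance in all arms, normally distributed changes and no dropout. The size of the shift is not in the documents.

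A second, smaller gap is that the between-arm laboratory test is specified on unadjusted changes, although the plan adjusts for baseline elsewhere.

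**What to change.** In the Synopsis (Statistical Analysis) and in Safety Analysis:

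1. Delete the paired t and signed-rank significance tests of laboratory change. Show the within-arm mean change with its 95% CI, labelled as description only.
2. Replace the ANOVA on changes with ANCOVA adjusted for the baseline value of the same parameter, consistent with the anticipated-outcomes paragraph. Report each dose minus placebo with a Dunnett-adjusted 95% CI.
3. State that any statement about the drug rests on these between-arm differences.

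The cost is a small change to the SAP wording and fewer p-values; no extra data are needed. The change does not control error across parameters. With 22 independent parameters each tested at 5%, the chance of at least one false between-arm finding is 1 − 0.95²² = 67.6%, so the laboratory results remain descriptive. It also does not resolve missing values after the Day 7 removals.

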### **Secondary Endpoints**

The secondary endpoints will include:

- Frequency, severity and relatedness of adverse events
  - Proportion of subjects with nausea and emesis
  - Proportion of subjects with diarrhea
  - Proportion of subjects who develop renal failure, encephalopathy or pulmonary compromise
  - Frequency of sepsis
- Changes in endotoxin levels adjusted for baseline levels at day 7 and 28
- Change in laboratory parameters

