### **Exploratory Endpoints**

[figure not shown]
The exploratory endpoints will include:

- sCD14 levels (ELISA test to be measured at VCU)
- Intestinal permeability Intestinal inflammation (stool calprotectin by ELISA -to be measured at VCU)
- Proportion meeting Lille criteria for futility (Lille score > 0.45) at day 7
- Mortality at day 7, day 30, day 90 and day 180

- Change in MELD score and discriminant function
- Change in liver function
- Intestinal microbiome-metagenome (end of treatment (EOT) comparison) 
- Activation of systemic inflammation: (EOT across group comparison, baseline-EOT comparison)
  - Markers of oxidative stress (measured at IU)
  - T-cell phenotypes (measured at IU)
  - Cytokines for specific T cell subtype and activation of innate immune system (measured at IU)
- Hepatic transcriptome (real time PCR, gene array Illumina in all cases-EOT across group analyses).RNA will also be available for baseline data and gene array with PCR confirmation of key targets will be performed so that variances at baseline across groups can be accounted for.

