## **Clinical Laboratory**

Clinical laboratory results will be summarized with descriptive statistics at baseline, each study time point, and with shifts from baseline.

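### Between-arm laboratory changes, a secondary endpoint with no parameter or visit named, are tested at 5% each with nothing covering the family of parameters, in a section that also calls laboratory safety descriptive

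*Combined protocol and SAP*

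**What the plan says.** The protocol's Secondary Endpoints section lists "Change in laboratory parameters" with no parameter, visit or summary measure. Its Exploratory Endpoints section separately lists "Change in liver function", which draws on part of the same blood panel.

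The Safety Analysis section begins: "Safety will be assessed by descriptive statistics of AEs and laboratory tests". It then prescribes inference. An "ANOVA model will be applied for testing the statistical significance of the difference in the changes in laboratory results between the study groups", and "Dunnett's method will be used for comparing each of the active groups to the Placebo group". It closes with a general rule: "All tests will be two-tailed, and a p value of" 5% or less counts as statistically significant. The Statistical Analysis part of the Synopsis also specifies ANOVA for "testing the statistical significance of the difference in the changes in laboratory results between the study groups", followed by Dunnett's method.

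None of these places names a visit for the laboratory ANOVA. The Clinical Laboratory section under the statistical methods does mention time points, but only for summaries: "Clinical laboratory results will be summarized with descriptive statistics at baseline, each study time point, and with shifts from baseline".

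Elsewhere the plan disclaims formal testing: for adverse events (primary endpoint paragraph), for cytokines and the microbiome (Interpretation of Labs), and for intestinal permeability (Other Mechanism of action related endpoints). Subgroup analyses are described as hypothesis-generating. The between-arm laboratory tests carry no such statement.

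**The concern.** The section gives two incompatible accounts of the laboratory data. Under one they are described. Under the other every parameter is tested between arms and any p at or below 5% is declared significant. Dunnett's method limits error over two comparisons (each dose against placebo) within a single parameter. It does nothing about looking at many parameters.

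Safety is the primary endpoint of this trial, laboratory change is secondary, and each arm has 22 patients. A chance difference could be reported as a toxicity signal. For a value such as bilirubin or INR it could equally be reported as benefit, and the Anticipated Outcomes paragraph already expects bilirubin to fall. Because no visit is named, the choice of visit is also open after the data are seen.

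The point concerns the between-arm tests only, not the within-arm paired tests.

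**Working it through.** **Plan's own figure.** The documents state no family-wise error rate for the laboratory tests, so there is none to reproduce. The only multiplicity figure elsewhere is the 0.025 in Determination of Sample Size, which belongs to the endotoxin comparison.

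**Inputs**

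- Parameters: the follow-up list in Laboratory Safety Parameters has 13 serum biochemistry items and 9 haematology items (white count with differential counted once, PT/INR counted once). 13 + 9 = 22.
- Arms: three, 22 patients each. Residual degrees of freedom per parameter: 3 × 22 − 3 = 63.
- Level: 5% two-sided per parameter, with the two dose comparisons handled by Dunnett.
- Visits: one test per parameter, because no text says more.
- Correlation between parameters: not in the documents; assumed, from 0 to 0.8.

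**Step 1: independent parameters.** With k tests at level 0.05 and no drug effect:

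P(at least one) = 1 − 0.95^k

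For k = 22: 1 − 0.95^22 = 1 − 0.3235 = 0.6765, about 68%. Expected number of false positives: 22 × 0.05 = 1.1. The chance passes one half at k = ln 0.5 / ln 0.95 = 13.5, that is, from 14 independent tests (51.2%).

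**Step 2: correlated parameters.** Null normal data were simulated for three arms of 22 and 22 parameters with a common correlation. The Dunnett rule declares significance if either dose-versus-placebo |t| exceeds 2.26 (the two-sided 5% value at 63 df). The ANOVA F test at 5% was simulated as a check.

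| Assumed correlation | Dunnett rule | ANOVA F test |
|---|---|---|
| 0 | 68% | 67% |
| 0.3 | 57% | 57% |
| 0.5 | 46% | 45% |
| 0.7 | not run | 32% |
| 0.8 | 26% | not run |

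Repeat Dunnett runs agree to within about two percentage points. An F-test run with assumed blocks of related values (red-cell indices, AST with ALT, BUN with creatinine, protein with albumin and calcium, bilirubin with INR) gave 61%. Correlation changes the chance of at least one false positive but not the expected number, which stays at about 1.1.

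**Step 3: more than one visit.** This is conditional, because the documents do not say it happens. If all 22 parameters were tested at two visits, the Dunnett rule gives 80% with correlation 0.3 between parameters and 0.5 between visits, 69% with 0.5 and 0.5, and 38% with 0.8 and 0.8.

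**Step 4: what full control would take.** Holding 22 parameters at 5% overall would need 0.05 / 22 = 0.0023 per parameter by Bonferroni. That would blunt a safety screen and is not proposed.

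**The case against.** The strongest reply is that the plan is inconsistent rather than confirmatory on laboratory values. The section opens descriptively, liver function change is also exploratory, the only stated null hypothesis concerns endotoxin, and formal testing is disclaimed for adverse events. No safety decision uses a laboratory p-value: abnormal values are judged by the investigator and by the numeric cutoffs in Table 1, and stopping the study rests on unexpected adverse events with DSMB and NIAAA guidance. In a phase 2a pilot, unadjusted safety comparisons favour sensitivity. Most of this stands. It limits the consequence to reporting and is a good reason not to ask for family-wise control. It does not explain why a section that calls itself descriptive then sets a significance threshold.

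Three stronger readings are tempting, and the documents do not support them:

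- **Testing at every visit.** The schedule draws bloods at D7, D30, D90 and D180, so a reader might infer 22 × 4 = 88 tests. No passage ties the ANOVA to each visit; only descriptive summaries are tied to time points. Where between-arm time points are named, they are day 7 and 30 for liver function (Analysis Population) or end of study (Anticipated Outcomes).
- **A false positive more likely than not.** For one test per parameter this holds under weak to moderate correlation but fails at about 0.5 or more.
- **A breach of the plan's own 5%.** That 5% is a per-test threshold. The plan claims no family-wise rate for laboratory tests.

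**Conclusion.** The point holds in a limited form. Between-arm laboratory changes are a secondary endpoint, are tested at 5% per parameter, and have no control across 22 parameters. The governing section contradicts itself on whether they are descriptive.

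With no drug effect and one test per parameter, the chance of at least one significant difference runs from about 26% (correlation 0.8) to 68% (independence), with about one false positive expected. These figures assume normal data, full arms of 22, no effect on any parameter, and a common correlation that the documents do not supply. Arm size matters little, because each test is held at 5% whatever the number of patients.

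The consequence is a false laboratory claim in the report, in either direction. It affects neither the endotoxin comparison nor any stopping decision. Because correcting it is a matter of wording, the change should be made.

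**What to change.** In the Statistical Analysis part of the Synopsis and in Safety Analysis:

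1. State that between-arm laboratory comparisons are descriptive.
2. Report each dose-minus-placebo mean difference with a 95% CI, naming the time points, together with the shifts from baseline already planned under Clinical Laboratory.
3. Call any p-value for these comparisons nominal, make no claim of statistical significance, and exempt them from the 5% sentence. Leave that sentence in place for the other tests it governs.
4. Reconcile the secondary listing of laboratory change with the exploratory listing of liver function change.
5. If the sponsor wants a tested laboratory endpoint, name one parameter and one visit under Secondary Endpoints.

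Do not use this edit to attach 5% to endotoxin. Its significance level has to be reconciled separately with the 0.025 in Determination of Sample Size.

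The cost is protocol and SAP wording. The same models are fitted, no new data are needed and no safety information is lost. The small downside is that laboratory differences can no longer be called statistically significant.

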## **Imm 124-E Hyperimmune Bovine Colostrum Powder**

### **Imm 124-E**

Imm 124-E contains hyperimmune bovine colostrum and is lactose- and fat-reduced, high in protein and contains no artificial additives. The product contains antibodies targeted against outer antigens of Enterotoxigenic *E. coli* (ETEC). Imm 124-E is harvested from the first milking of dairy cows that have been immunized with a killed ETEC to produce high levels of specific antibodies against selected surface antigens from the most common strains of ETEC, the main causative agent of Traveler's diarrhea. Immuron hyperimmune colostrum powder contains approximately 30% antibodies (immunoglobulins) in the dry powder. The main classes of immunoglobulins found in bovine colostrum are IgG (mainly IgG1) and IgA with small amounts of IgM and IgE. The immunoglobulins in Imm 124-E have high binding activity against the lipopolysaccharide (LPS) of Gram-negative bacteria. Binding of LPS is assayed by Immuron using a standardized ELISA and immuno-blotting detection systems, the Immuron's hyperimmune colostrum powder product.

Imm 124-E is currently marketed as a complimentary medicine through pharmacies in Australia under the name Travelan®. It has been sold since September 2004 for the prevention of traveler's diarrhea at a dose of 200mg three times a day for use by adults and children over 6 years of age. Approximately 140,000 packets (30 tablets each packet) have been sold and no treatment related adverse events have been reported.

In 2001 Immuron Ltd provided full risk assessment information to the Australian Therapeutic Goods Administration (TGA) and Imm 124-E was approved by the TGA as suitable for use as an active ingredient in listable therapeutic goods and a compositional guideline was published in September 2003. Immuron's Imm 124-E Bovine Colostrum Powder is produced to international dairy GMP standards suitable for export of product for human consumption and export from Australia. These standards are recognized in the USA.

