## **Data Safety Monitoring Board**

An independent Data and Safety Monitoring Board (DSMB) to be established by the NIH and TREAT consortium to assess at intervals the progress of a clinical trial, the safety data, and the critical safety endpoints, and to recommend to the NIH whether to continue, modify, or stop a trial.

**Anticipated Outcomes:** Means for continuous variables at end of study will be analyzed adjusting for baseline values using ANCOVA. Proportions will be compared using chi square or Fisher's Exact test. We expect to show a greater decrease in mean circulating LPS levels in those receiving Steroids+ Imm 124-E compared to steroids + placebo. We further expect to demonstrate that those receiving Imm 124-E will have a reduction in MELD, DF, intestinal permeability, markers of intestinal inflammation, markers of dendritic cell activation, pro-inflammatory T-cell and cytokine profile, cholestasis (serum bile acids) and bilirubin.

**Additional pathophysiologic insights:** Microbiome-metagenomic-immunologic-transcriptomic-histologic data from will lend themselves to analyses using a "systems biology approach" to determine how interactions between these contribute to severe AH and how Imm 124-E can modify this. These will provide novel insights on the role of the metagenome in AH and provide additional targets for therapy in the future.

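### The example kit for anti-bovine IgG is a bovine-IgG kit stated not to react with human IgG, so if used it would measure absorbed product, not the subject's antibody response

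*Combined protocol and SAP*

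**What the plan says.** The last paragraph of the Safety Analysis section (Combined protocol and SAP) plans "The measurement of serum bovine and anti-LPS antibody levels at baseline, Day 7, and Day 28-30" and an assessment of fold increases over baseline. It adds: "Typically, an antigenic response is defined as 4-fold above baseline".

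On method it says: "A specialist laboratory can utilize commercially available ELISAs" "to measure for the presence of serum anti-bovine and anti-LPS IgGs". Two examples follow. The first is introduced as "such as the bovine IgG ELISA kit from Genway (no reactivity with IgG from mouse, human, rat and rabbit"); the second is a "human LPS ELISA kit from Cusabio, respectively". The closing word of that second quote pairs the first kit with anti-bovine IgG and the second with anti-LPS IgG. All samples are to be run together once the study has ended.

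The section describing Imm 124-E says that the powder "contains approximately 30% antibodies (immunoglobulins) in the dry powder", mainly IgG and IgA, and that these immunoglobulins bind LPS strongly.

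**The concern.** An antigenic response in a trial subject is antibody made by that subject, that is, human IgG directed at bovine protein or at LPS. The first example kit is described as blind to human IgG. It therefore fits a different question: how much bovine immunoglobulin has reached the blood.

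If the laboratory follows the example, two errors become possible. A real human anti-bovine response would go unseen. And bovine IgG absorbed from the product, rising from a low baseline, could be read as an antigenic response. The second error could also look dose-related, because the active arms swallow different amounts of bovine immunoglobulin.

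The anti-LPS part raises a related question. The second kit is named for LPS, the antigen, and not for an antibody against it. Even a true anti-LPS antibody assay would need to separate species, since the product itself carries bovine antibody that binds LPS.

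**Working it through.** The plan gives no power, rate or threshold derivation for this measurement, so there is no figure to reproduce. The check is mainly a comparison of what is to be measured with what each example kit is said to measure.

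**1. Bovine part**

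| Element of the paragraph | Analyte it implies |
|---|---|
| Opening sentence (bovine antibody in serum) | bovine IgG, i.e. absorbed product |
| Mention of an antigenic response | human antibody |
| Stated targets (anti-bovine IgG) | human antibody |
| Example kit (bovine IgG, no reactivity with human IgG) | bovine IgG only |

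The kit agrees with the opening sentence and conflicts with the next two elements. One kit with that specificity cannot serve both purposes, and the paragraph does not say which is meant. This follows from the plan's own description of the kit and needs no outside source.

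**2. Could uptake alone look like a dose-related response?**
Inputs: about 30% immunoglobulin in the powder (Imm 124-E section); 2400 and 4800 mg/day (Synopsis, Treatment).
- Group A: 0.30 x 2400 = 720 mg/day of product immunoglobulin.
- Group B: 0.30 x 4800 = 1,440 mg/day.
- Group C: none from Imm 124-E. The placebo is a milk-protein powder whose immunoglobulin content is not stated.

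Intake doubles between the active arms. The plan also cites increased intestinal permeability in alcoholic liver disease (Other Mechanism of action related endpoints). A dose-ordered rise in bovine IgG is therefore plausible with no host response at all. The documents give no serum bovine IgG levels and no assay limit, so the size of such a rise cannot be calculated.

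**3. LPS part, illustration only**
Suppose the second kit does measure LPS. The plan expects LPS to fall: "We expect to show a greater decrease in mean circulating LPS levels in those receiving Steroids+ Imm 124-E" compared with placebo (Anticipated Outcomes, under Data Safety Monitoring Board). Table 4, Scenarios 2 and 4, assumes mean drops of 50% on active drug and 25% on placebo, each with SD 25%.
- Mean fold change = 1 - drop: active 1 - 0.50 = 0.50; placebo 1 - 0.25 = 0.75.
- A 4-fold level corresponds to a drop of -300%. Distance from the mean = (mean drop + 300) / SD: active (50 + 300) / 25 = 14 SD; placebo (25 + 300) / 25 = 13 SD.

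Under a normal approximation the expected response rate is about 0 in every arm, whatever antibody the subjects made. This shows only why the kit's analyte matters. It does not show what the kit detects.

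**4. Number of samples**
66 subjects x 3 time points = 198, if every subject gives all three samples.

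**The case against.** The strongest reply is that nothing is fixed. The wording is permissive, the kits are examples, and a specialist laboratory may choose others. The 4-fold rule is described as typical and is not adopted as a responder definition; the only commitment is to assess fold increases. Both points stand, so every consequence here is conditional on the example kits being used.

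A second reply is that the plan meant absorbed bovine antibody, as the opening sentence can be read. The first kit's lack of human cross-reactivity would then be a strength, and the slip would be one prefix. The reading is possible, but it does not make the paragraph sound: a fold rise in bovine IgG is not an antigenic response, and the stated targets would still be wrong.

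A reader might also infer three stronger things that the documents do not support.
- *All 198 samples will be scored on the wrong analyte.* The kits are not binding. The count is also an upper bound: subjects meeting the Lille failure criteria at Day 7 are removed from the study, and the Current Treatment section cites mortality above 40% in severe disease.
- *The primary safety endpoint would give false reassurance.* That endpoint is analysed through the incidence and severity of adverse events. Antibody levels appear in none of the primary, secondary or exploratory endpoint lists. Immune-type reactions are also looked for through the graded systemic symptom scale and, as optional exploratory tests, complement activation and immune complexes.
- *The LPS kit would merely repeat the endotoxin measurement.* This rests on the kit's name alone. The plan pairs it with anti-LPS IgG, so the name may be shorthand.

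**Conclusion.** The concern holds for the bovine part. The plan's example method cannot measure its stated target, by the plan's own description of that method, and the paragraph is inconsistent about the analyte. This is more than missing laboratory detail, because the only assay guidance given points to the wrong quantity for an antigenic response. For the LPS part, the most that can be said is that the kit's analyte needs confirming.

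The reach is limited. This is a supplementary safety measurement of up to 198 samples. Adverse event counts, the endotoxin ANCOVA, the sample size and the error rates do not change. The conclusion assumes that the laboratory follows the bovine example and that a fold rise is read as a response by the subject. That baseline bovine IgG is near zero, which would make fold rises unstable, is an assumption that the documents neither confirm nor exclude.

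**What to change.** Revise the antibody paragraph in the Safety Analysis section as follows.
- Name the immunogenicity targets as human anti-bovine IgG and human anti-LPS IgG, measured by assays that detect human IgG specifically. Species specificity is needed because the product carries bovine IgG that binds LPS.
- Apply any 4-fold criterion only to these two measurements, with a stated rule for values below the assay limit.
- If the bovine-IgG kit is kept, report its result by arm as systemic exposure to product, not as an antigenic response.
- Confirm from the insert what the second example kit detects, and keep it only if it measures human anti-LPS IgG.
- Reconcile the paragraph with Table 2, which lists no serum anti-bovine or anti-LPS antibody sample.

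The cost is protocol wording and possibly a different assay, which may need brief qualification where an off-the-shelf kit would not. Because the samples are analysed together at study end, the assay can be settled before any result exists, with no change to treatment or visits.
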